4.3. Safety Analysis Set

The safety analysis set (SAFETY) will include all subjects who were randomized and received at least one dose of the investigational product (ie, tofacitinib or placebo). Subjects will be analyzed in the treatment groups as they received. If a subject is treated but not randomized, then the subject will be excluded from the SAFETY analysis set. A narrative will be provided for this subject in the CSR.

4.4. Other Analysis Sets

4.4.1. Endpoint Specific Analysis Sets

Subjects will be excluded from the FAS for analyzing a specific endpoint if the criterion for inclusion is not met for the endpoint.

Table 2. Endpoint Specific Analysis Sets

Endpoint	Inclusion	Rationale
ASDAS _{CRP} Clinically Important Improvement (improvement [decrease] from Baseline in ASDAS _{CRP} ≥ 1.1 units)	Include subjects with Baseline ASDAS _{CRP} ≥ 1.1 units in FAS	Restrict Baseline ASDAS _{CRP} ≥ 1.1 units to allow room for response
ASDAS _{CRP} Major Improvement (improvement [decrease] from Baseline in ASDAS _{CRP} ≥ 2.0 units)	Include subjects with Baseline ASDAS _{CRP} ≥ 2.0 units in FAS	Restrict Baseline ASDAS _{CRP} ≥ 2.0 units to allow room for response
ASDAS _{CRP} Inactive Disease (ie, ASDAS _{CRP} < 1.3 units)	Include subjects with Baseline ASDAS _{CRP} ≥ 1.3 units in FAS	Restrict Baseline ASDAS _{CRP} ≥ 1.3 units to allow room for response
Δ in Swollen Joint Count (44)	Include subjects with Baseline swollen joint count (44) > 0 in FAS	Having swollen joints is not an enrollment criterion, it is expected only a subset of subjects will have swollen joints at Baseline.
Δ MASES	Include subjects with Baseline MASES > 0 in FAS	Enthesitis is not an enrollment criterion, it is expected only a subset of subjects will have enthesitis at Baseline.
Abbreviations: Δ = change from Baseline, ASDAS _{CRP} = Ankylosing Spondylitis Disease Activity Score - C-Reactive Protein, FAS = Full Analysis Set, MASES = Maastricht Ankylosing Spondylitis Enthesitis Score.		

5. GENERAL METHODOLOGY AND CONVENTIONS

There will be a total of 2 planned analyses conducted when all applicable subjects have completed their Week 16 and Week 48 (including follow-up) visits, respectively. The investigators, subjects and sponsor study team will remain blinded to the first 16 weeks of treatment assignment through the entire duration of the trial until database release at Week 48. The Week 16 analysis will include all efficacy data through Week 16 and the safety data through the data cutoff date (for those subjects who have passed the Week 16 visit). As the primary endpoint (ASAS20), the key secondary endpoint (ASAS40) and the other Type I error controlled secondary endpoints are at Week 16, there will be no additional adjustment made for Type I error rate at the final analysis at Week 48. The efficacy analysis results through Week 16 obtained from the Week 16 analysis will be considered final and definitive. CCI

The Week 48 analysis will be conducted when all the applicable subjects have completed their Week 48 (including follow-up) visit and the database is released. All the Week 48 analysis results will be secondary in nature. The Week 48 analysis will contain results for earlier visits prior to or at Week 16 including those for the primary endpoint and the key secondary endpoint; however, they will serve as a sensitivity analysis only to ensure there are

no major changes to the definitive results for the primary endpoint and the key secondary endpoint obtained at the Week 16 analysis.

5.1. Hypotheses and Decision Rules

This protocol is designed to establish the superiority of tofacitinib 5 mg BID to placebo for the treatment of active AS based on the primary endpoint of ASAS20 at Week 16 in subjects who have had an inadequate response to previous treatments.

All statistical tests will be conducted at the 2-sided 5% (or equivalently 1-sided 2.5%) significance level for comparing tofacitinib 5 mg BID to placebo. Type I error will be controlled at 2-sided 5% or equivalently 1-sided 2.5%.

For the primary endpoint of ASAS20 at Week 16, if the 2-sided p-value is $\leq 5\%$, the superiority of tofacitinib 5 mg BID to placebo will be declared for this primary endpoint and the primary objective of this study is met.

Hypothesis testing will continue to the global family of select set of secondary endpoints stated below [Global Type I Error Control (for the primary endpoint and a select set of secondary endpoints)]. For each of the endpoints within this family, superiority of tofacitinib 5 mg BID to placebo will be declared if statistical significance is achieved under the step-down testing procedure.

In addition, three other families of hypotheses, ASAS family endpoints (Type I Error Control for Endpoints in the ASAS Family), ASAS20's earlier time points (Type I Error Control for ASAS20 at Earlier Time Points) and ASAS40's earlier time points (Type I Error Control for ASAS40 at Earlier Time Points) will also be tested. For each of the endpoints or time points of ASAS20/ASAS40, superiority of tofacitinib 5 mg BID to placebo will be declared if statistical significance is achieved under its respective step-down testing procedure.

Global Type I Error Control (for the primary endpoint and a select set of secondary endpoints): The family-wise Type I error rate will be controlled at the 2-sided 5% (or equivalently 1-sided 2.5%) significance level using a step-down testing procedure for the primary endpoint of ASAS20 at Week 16, the key secondary endpoint of ASAS40 at Week 16, and a select set of secondary endpoints at Week 16 tested in the sequence below: ASAS20, ASAS40, Δ ASDAS_{CRP}, Δ hsCRP, Δ ASQoL, Δ SF-36v2 Physical Component Summary (PCS), Δ BASMI, and Δ FACIT-F Total Score. When an endpoint fails to declare statistical significance, this endpoint and the remaining endpoints lower in the hierarchy will be considered non-significant. The rationale for the selection and ordering of the select set of secondary endpoints are clinical importance, precedence and likelihood of statistical success based on the results of the A3921119 study.

Type I Error Control for Endpoints in the ASAS Family: Δ PGA, Δ in total back pain, Δ BASFI, and Δ in inflammation (average of questions 5 and 6 of BASDAI) are the 4 ASAS components used in deriving ASAS20, thus they are considered belonging to the ASAS family of endpoints. A step-down testing procedure will be applied to them and tested in the sequence below: ASAS20, Δ PGA, Δ in total back pain, Δ BASFI, and Δ in inflammation (average of questions 5 and 6 of BASDAI) at Week 16. When an endpoint fails to declare

statistical significance, this endpoint and the remaining endpoints lower in the hierarchy will be considered non-significant. Though this testing scheme does not protect the Type I error for the family of all possible comparisons, it will provide Type I error protection for testing the family of ASAS endpoints.

Type I Error Control for ASAS20 at Earlier Time Points: In order to be more rigorous about establishing the onset of efficacy as measured by ASAS20 at the earliest time point at which there is statistical separation between tofacitinib 5 mg BID and placebo, a step-down approach with the ASAS20 from Week 16 to earlier time points (order of testing: Weeks 16, 12, 8, 4, and 2) will also be used for each time point. Though this testing scheme does not protect the Type I error for the family of all possible comparisons, it will provide Type I error protection for testing the family of ASAS20 time points.

Type I Error Control for ASAS40 at Earlier Time Points: In order to be more rigorous about establishing the onset of efficacy as measured by ASAS40 at the earliest time point at which there is statistical separation between tofacitinib 5 mg BID and placebo, a step-down approach with the ASAS40 from Week 16 to earlier time points (order of testing: Weeks 16, 12, 8, 4, and 2) will also be used for each time point. Though this testing scheme does not protect the Type I error for the family of all possible comparisons, it will provide Type I error protection for testing the family of ASAS40 time points.

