The family-wise Type I error rate will be controlled at the 2-sided 5% (or equivalently 1-sided 2.5%) significance level using a step-down testing procedure for the primary endpoint of ASAS20, the key secondary endpoint of Assessment of the SpondyloArthritis International Society $\geq 40\%$ improvement (ASAS40) and a select set of secondary endpoints at Week 16 tested in the sequence below: ASAS20, ASAS40, change from baseline in Ankylosing Spondylitis Disease Activity Score (ASDAS_{CRP}), change from baseline in High Sensitivity C-Reactive Protein (hsCRP), change from baseline in Ankylosing Spondylitis Quality of Life (ASQoL), change from baseline in SF-36 Health Survey Version 2, Acute (SF-36v2) Physical-Component Summary (PCS), , and change from baseline in Bath Ankylosing Spondylitis Metrology Index (BASMI), and change from baseline in Functional

Assessment of Chronic Illness Therapy-Fatigue (FACIT-F) Total score (See [Section 9.2.3](#) for additional Type I error control procedures).

There will be a total of 2 planned analyses conducted when all applicable subjects have completed their Week 16 and Week 48 (including follow-up) visits, respectively. CCI

(see [Section 9.2](#) for details).

SCHEDULE OF ACTIVITIES

The Schedule of Activities table provides an overview of the protocol visits and procedures. Refer to [STUDY PROCEDURES \(Section 6\)](#) and [ASSESSMENTS \(Section 7\)](#) for detailed information on each procedure and assessment required for compliance with the protocol.

The investigator may schedule visits (unplanned visits) in addition to those listed on the schedule of activities table, in order to conduct evaluations or assessments required to protect the well-being of the subject.

Protocol Activity Visit Window (days)	Screening ¹	Treatment Period										Follow -up ¹¹
	30 days	Baseline Day 1	Week 2	Week 4	Week 8	Week 12	Week 16	Week 24	Week 32	Week 40	Week 48	
			±3	±3	±7	±7	±7	±7	±7	±7	±7	
Informed Consent/Assent	X											
AS Diagnosis ²	X	X										
Demographics	X											
General Medical History (includes previous vaccinations, family history of AS, herpes zoster history, smoking and alcohol use, CV)	X											
Determination of “bDMARD-naïve” or “TNFi-IR” status		X										
Complete Physical Exam ³	X	X					X				X	
Targeted Physical Exam ⁴			X	X	X	X		X	X	X		X
Height, Weight ⁵ and Waist circumference ⁵	X	X	X	X	X	X	X	X	X	X	X	X
Vital Signs (blood pressure, pulse rate, temperature)	X	X	X	X	X	X	X	X	X	X	X	X

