9.2.3. Control for Type I Error Rate

This protocol is designed to establish the superiority of tofacitinib 5 mg BID to placebo for the treatment of active AS based on the primary endpoint of ASAS20 at Week 16 in subjects who have had an inadequate response to previous treatments.

All statistical tests will be conducted at the 2-sided 5% (or equivalently 1-sided 2.5%) significance level for comparing tofacitinib 5 mg BID to placebo. Type I error will be controlled at 2-sided 5% or equivalently 1-sided 2.5%.

For the primary endpoint of ASAS20 at Week 16, if the 2-sided p value is $\leq 5\%$, the superiority of tofacitinib 5 mg BID to placebo will be declared for this primary endpoint and the primary objective of this study is met. Hypothesis testing will continue to the global family of select set of secondary endpoints stated below (*Global Type I Error Control (for the primary endpoint and a select set of secondary endpoints)*). For each of the endpoints within this family, superiority of tofacitinib 5 mg BID to placebo will be declared if statistical significance is achieved under the step-down testing procedure. In addition, three other families of hypotheses, ASAS family endpoints (*Type I Error Control for Endpoints in the ASAS Family*), ASAS20's earlier time points (*Type I Error Control for ASAS20 at Earlier Time Points*) and ASAS40's earlier time points (*Type I Error Control for ASAS40 at Earlier Time Points*) will also be tested. For each of the endpoints or time points of ASAS20/ASAS40, superiority of tofacitinib 5 mg BID to placebo will be declared if statistical significance is achieved under its respective step-down testing procedure.

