Global Type I Error Control (for the primary endpoint and a select set of secondary endpoints): The family-wise Type I error rate will be controlled at the 2-sided 5% (or equivalently 1-sided 2.5%) significance level using a step-down testing procedure for the primary endpoint of ASAS20, the key secondary endpoint of ASAS40 and a select set of secondary endpoints at Week 16 tested in the sequence below: ASAS20, ASAS40, change from baseline in ASDAS_{CRP}, change from baseline in hsCRP, change from baseline in ASQoL, change from baseline in SF-36v2 Physical Component Summary (PCS), change from baseline in BASMI, and change from baseline in the FACIT-F Total score. When an endpoint fails to declare statistical significance, this endpoint and the remaining endpoints lower in the hierarchy will be considered non-significant. The rationale for the selection and ordering of the select set of secondary endpoints are clinical importance, precedence and likelihood of statistical success based on the results of the A3921119 study.

Type I Error Control for Endpoints in the ASAS Family: Δ in Patient Global Assessment (PGA) of disease, change from baseline in total back pain, Δ BASFI, and change from baseline in inflammation (average of questions 5 and 6 of BASDAI) are the 4 ASAS components used in deriving ASAS20, thus they are considered belonging to the ASAS family of endpoints. A step-down testing procedure will be applied to them and tested in the sequence below: ASAS20, change from baseline in PGA, change from baseline in total back pain, change from baseline in BASFI, and change from baseline in inflammation (average of questions 5 and 6 of BASDAI) at Week 16. When an endpoint fails to declare statistical significance, this endpoint and the remaining endpoints lower in the hierarchy will be considered non-significant. Though this testing scheme does not protect the Type I error for the family of all possible comparisons, it will provide Type I error protection for testing the family of ASAS endpoints.

Type I Error Control for ASAS20 at Earlier Time Points: In order to be more rigorous about establishing the onset of efficacy as measured by ASAS20 at the earliest time point at which

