there is statistical separation between tofacitinib 5 mg BID and placebo, a step-down approach with the ASAS20 from Week 16 to earlier time points (order of testing: Weeks 16, 12, 8, 4, and 2) will also be used for each time point. Though this testing scheme does not protect the Type I error for the family of all possible comparisons, it will provide Type I error protection for testing the family of ASAS20 time points.

Type I Error Control for ASAS40 at Earlier Time Points: In order to be more rigorous about establishing the onset of efficacy as measured by ASAS40 at the earliest time point at which there is statistical separation between tofacitinib 5 mg BID and placebo, a step-down approach with the ASAS40 from Week 16 to earlier time points (order of testing: Weeks 16, 12, 8, 4, and 2) will also be used for each time point. Though this testing scheme does not protect the Type I error for the family of all possible comparisons, it will provide Type I error protection for testing the family of ASAS40 time points.

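### Could the ASAS40 time-point chain declare ASAS40 at Week 16 after the primary ASAS20 test has failed?

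*SAP*

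**What the plan says.** Every test is at two-sided 5%. The global sequence in SAP 5.1 and Protocol 9.2.3 runs from ASAS20 to ASAS40 and then to six further endpoints, all at Week 16. Its stop rule reads: "When an endpoint fails to declare statistical significance, this endpoint and the remaining endpoints lower in the hierarchy will be considered non-significant".

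Three more families follow:

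- **ASAS components.** These are "tested in the sequence below: ASAS20, change from baseline in PGA, change from baseline in total back pain", then BASFI and inflammation.
- **ASAS20 over time.** This is "a step-down approach with the ASAS20 from Week 16 to earlier time points".
- **ASAS40 over time.** This is "a step-down approach with the ASAS40 from Week 16 to earlier time points (order of testing: Weeks 16, 12, 8, 4, and 2").

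For these families, "superiority of tofacitinib 5 mg BID to placebo will be declared if statistical significance is achieved under its respective step-down testing procedure". Each carries a statement that it does not protect error over all possible comparisons.

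Protocol 9.2.3 introduces the secondary testing by saying that, if the primary p-value is at most 5%, "the primary objective of this study is met. Hypothesis testing will continue to the global family of select set of secondary endpoints stated below". The same paragraph then adds the three other families. The Protocol Summary (Statistical Methods) refers the reader to Section 9.2.3 "for additional Type I error control procedures".

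**The concern.** ASAS40 at Week 16 sits in two chains. In the global sequence it is second, behind ASAS20. In the ASAS40 time-point chain it is first, with nothing ahead of it. The other three chains name ASAS20 as their first step, so a failed primary closes them by construction. The ASAS40 chain does not name it, and no entry condition is written.

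Suppose ASAS20 misses and ASAS40 reaches p ≤ 0.05. The global rule says ASAS40 is non-significant. The time-point family, taken alone, says superiority is declared and testing moves on to Week 12. At stake would be a claim on the key secondary endpoint, and an onset claim at Weeks 12 to 2, after a failed primary.

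**Working it through.** **1. The plan's own figure.** Inputs from Protocol 9.1: 120 per arm, ASAS20 40% vs 60%, two-sided 5%, power about 89%.

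- SE = √(0.4×0.6/120 + 0.6×0.4/120) = 0.0632
- 0.20/0.0632 = 3.162, and 3.162 − 1.960 = 1.202
- Power = Φ(1.202) = 88.5% (87.7% with a pooled variance)

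This agrees with the stated figure. Simulating the stratified test of SAP 5.2.1.1 with 96 and 24 per arm, the primary misses in 11.7% of trials at the planned effect.

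**2. The four chains side by side.**

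| Chain | First hypothesis | Closed by a failed ASAS20? |
|---|---|---|
| Global | ASAS20 Week 16 | Yes |
| ASAS components | ASAS20 Week 16 | Yes |
| ASAS20 time points | ASAS20 Week 16 | Yes |
| ASAS40 time points | ASAS40 Week 16 | Not by its own first step |

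**3. The Week 16 outcomes.**

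| ASAS20 | ASAS40 p ≤ 0.05 | Global verdict on ASAS40 | Do the two readings of the time-point chain agree? |
|---|---|---|---|
| succeeds | yes | significant | Yes, chain proceeds |
| succeeds | no | non-significant | Yes, chain stops |
| fails | no | non-significant | Yes, chain stops |
| fails | yes | non-significant | Only here could they differ |

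In the last row the two chains refer to one hypothesis, tested with the same data, analysis set and method. The stop rule gives that hypothesis a verdict. If it is non-significant, a step-down beginning there ends there. The ungated route needs the same hypothesis to be significant and non-significant at once.

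**4. Size if the ungated route were used anyway.** ASAS40 responders are a subset of ASAS20 responders, so under the null the two Z statistics have correlation r = √[p40(1−p20) / (p20(1−p40))]. The p40 values are assumptions. The chance that either statistic exceeds 1.96, from the bivariate normal:

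| p20 / p40 | r | One-sided | Two-sided |
|---|---|---|---|
| 40% / 20% | √(0.12/0.32) = 0.612 | 4.35% | 8.71% |
| 30% / 25% | √(0.175/0.225) = 0.882 | 3.60% | 7.20% |
| 45% / 10% | √(0.055/0.405) = 0.369 | 4.70% | 9.39% |

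Independent tests would give 1 − 0.95² = 9.75% two-sided. In simulation of the SAP's stratified test with its 0.5/1 correction (1,000,000 null trials each), the ungated route adds 1.91 points one-sided to the ASAS20 test alone at 40/20, 1.14 at 30/25 and 2.26 at 45/10.

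**5. How often the last row of step 3 would arise.** With ASAS20 at 40% vs 60%, it occurs in 8.2% of all trials if ASAS40 is 20% vs 40%. Over assumed ASAS40 placebo rates of 10–25% and differences of 10–20 points, it occurs in 0.5% (25 vs 35) to 10.7% (10 vs 30). Tofacitinib works on both endpoints in these scenarios, so these are frequencies of the situation and not error rates.

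**6. Under the gated reading.** ASAS40 can be declared only after ASAS20. The chance of any false claim on the pair is at most 5% two-sided, and the chance of an ASAS40 claim after a failed ASAS20 is zero.

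**The case for a change.** The best opposing case is textual. The sentence adding the three families contains no condition, and tying each family to its own step-down suggests that each stands alone. The authors wrote ASAS20 into the component chain, so they could have written it here. The disclaimer about all possible comparisons covers different hypotheses in parallel families. It does not obviously license two verdicts on one hypothesis. SAP 6.3 also treats ASAS40 at the earlier visits as error-controlled, so an onset claim would carry that status. And the disputed outcome becomes common if the true ASAS20 effect is modest: at 40% vs 50%, it occurs in about 41% to 59% of trials when ASAS40 is 15–20% on placebo and 30–35% on tofacitinib.

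What stands is that the entry condition is implied and not written. The rest does not carry the point. A free-standing chain still cannot overturn a verdict that the global rule has fixed on its first member. The family is named for earlier time points and exists to date the onset of response. Week 16 is its anchor, as it is in the ASAS20 family, where the Week 16 step merely restates the primary result. SAP 2.1.1 and Table 8 give ASAS40 at Week 16 its own role as key secondary and label the other visits secondary. The 41–59% figure uses half the planned ASAS20 difference and again counts situations, not errors.

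**Conclusion.** The concern does not call for a change. The omission is real, but the plan's stop rule supplies the missing condition, and the order of presentation in Protocol 9.2.3 points the same way. An analyst following both documents would carry the global result for ASAS40 at Week 16 into the time-point chain, and would test Weeks 12, 8, 4 and 2 only if that result was significant.

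On that reading the primary test, its power and the 5% two-sided control of the global family are untouched. The 3.6–4.7% one-sided figures describe a route that the global rule bars. They also rest on assumed ASAS40 rates, and they measure error across parallel families, which the plan says it does not control. Writing the condition down would be harmless editing, but it would alter no analysis or permitted claim.

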5.2. General Methods

As subjects randomized to treatment group of placebo → tofacitinib 5 mg BID (ie, → means switching to) will advance from placebo to open-label treatment of tofacitinib 5 mg BID at Week 16, the treatment label used for reporting visits up to Week 16 will be “Placebo” and treatment label for reporting visits after Week 16 through Week 48 will be “Placebo → Tofacitinib 5 mg BID”. For analyses through Week 16, the following treatment comparison will be made at each time point, where applicable:

- Tofacitinib 5 mg BID vs. Placebo.

For analyses after Week 16 through Week 48, the following treatment comparison will be made at each time point,

- Tofacitinib 5 mg BID vs. Placebo → Tofacitinib 5 mg BID.

The primary efficacy comparison for the primary endpoint of ASAS20 will be between tofacitinib 5 mg BID and placebo at Week 16.

Descriptive Summaries

In general, the data for all continuous endpoints will be summarized by treatment group (ie, 2 groups) and by time point in tables containing descriptive statistics (N [which is the number of subjects evaluable for the endpoint at the time point], mean, standard deviation, standard error of the mean, minimum, 1st, 2nd (ie, median) and 3rd quartiles and maximum) for actual and change from Baseline (or percent change from Baseline) values for those endpoints measured at Baseline. In case when N=1 (ie, only one subject is

available/evaluable for summary), standard deviation and standard error will be reported as “NA” (not applicable) while the remaining statistical parameters will have the same value as the mean. The data for all response-type endpoints will be summarized by treatment group and by time point in tables showing descriptive statistics: N, n (ie, number of responders), response rate (%), standard error of the response rate, and 95% confidence interval (CI) based on normal approximation. If \hat{p} is the estimated response rate, then the 95% CI is calculated as:

$$\hat{p} \pm z_{0.975} \sqrt{\frac{\hat{p}(1 - \hat{p})}{N}}$$

where $z_{0.975}$ is the 97.5th percentile of the standard normal distribution and N is the number of subjects evaluable for the endpoint at the time point. If the lower bound is calculated to be negative, it will be set to 0%; if the upper bound is calculated to be larger than 100%, it will be set to 100%. In case when response rate is 0 or 100%, standard error will be reported as “NA” and the 95% CI bounds will be the same as the response rate. The displays described above for continuous and response-type endpoints will only use available data with no imputation. Therefore, the calculation of response rates will use the number of evaluable subjects as denominators.

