9.1. Sample Size Determination

The primary efficacy analysis is to compare the ASAS20 response rate at Week 16 of the tofacitinib 5 mg BID and placebo via the normal approximation for the difference in binomial proportions. Assuming a placebo response rate of 40% for ASAS20 response at Week 16, a sample size of 120 per arm will yield about 89% power to detect a difference of at least 20% between tofacitinib 5 mg BID and placebo at a two-sided significance level of 5%. In the Phase 2 proof of concept trial A3921119, ASAS20 response rates at Week 12 were 63% and 40% for tofacitinib 5 mg BID and placebo, respectively.

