If there is no (ie, 0) response or 100% response in any one or both of the two treatment groups for the comparison in a stratum, eg, tofacitinib 5 mg BID vs. placebo, when calculating the proportions above, 0.5 will be added to the number of responses (ie, numerator) and 1 will be added to the denominator in each treatment in that stratum corresponding to the pair of comparison for calculating the treatment difference, standard error (ie, $\sqrt{\text{var}(d)}$), 95% CI and 2-sided p-value (Agresti, 2002).⁵

When response rate of 0% or 100% is observed in both treatments in comparison and in both strata, no formal comparison will be performed. Estimated response rate of 0% or 100% will be reported as observed. Standard error will be reported as 0.

The final results will be expressed in percentages, ie, (proportions x 100)%.

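### By-arm 95% confidence intervals for response rates have zero width when the observed rate is 0% or 100%; at 0/120 the exact upper limit is 3.0% (descriptive displays only)

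*SAP*

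**What the plan says.** SAP 5.2 sets out the descriptive displays. "The data for all response-type endpoints will be summarized by treatment group and by time point in tables showing descriptive statistics", among them a "95% confidence interval (CI) based on normal approximation". The limits are the estimated rate plus or minus a normal multiplier times the usual binomial standard error; the multiplier "is the 97.5th percentile of the standard normal distribution and N is the number of subjects evaluable for the endpoint at the time point". Limits that fall below 0% or above 100% are truncated. Nothing is imputed: "the calculation of response rates will use the number of evaluable subjects as denominators".

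The boundary case has its own instruction. If no subject or every subject in the arm responds, the standard error is shown as NA, while "the 95% CI bounds will be the same as the response rate".

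Treatment comparisons are handled differently. Under SAP 5.2.1.1, if either arm in a stratum has no responders or only responders, 0.5 is added to the numerator and 1 to the denominator of both arms in that stratum before the difference, its standard error, the interval and the p-value are computed. Only if both arms are at 0% or 100% in both strata is there no formal comparison, and then "Standard error will be reported as 0".

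SAP 6.3 applies the Section 5.2 descriptive display to the secondary binary endpoints, including ASAS partial remission, ASDAS major improvement and ASDAS inactive disease, from Week 2 onward.

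**The concern.** Observing no responders does not show that the true rate is zero. The normal-approximation interval fails here because its estimated variance is p(1−p)/N, which is exactly zero at p = 0 or p = 1. The SAP foresees the case and prescribes the degenerate result, so this is a stated rule and not a gap in detail.

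At stake is the accuracy of a column labelled as a 95% confidence interval. A cell printed as 0% to 0% claims a precision that the data do not have, and it could be carried from the tables into the study report. The endpoints most exposed are the strict ones at early placebo visits: partial remission needs a score of 2 or less in all four domains, and inactive disease needs ASDAS below 1.3, in subjects who enter with BASDAI of at least 4.

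**Working it through.** **Inputs.**
- N = 120 per arm. Protocol 9.1 states that "a sample size of 120 per arm will yield about 89% power to detect a difference of at least 20" percentage points over a 40% placebo rate. Evaluable N can only be this or smaller.
- z = 1.96, two-sided 95% (SAP 5.2).
- Display by treatment group and time point (SAP 5.2).
- True rates of 1%, 2% and 3% for strict endpoints are my assumptions.

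**The plan's own figure.** For 60% versus 40% with 120 per arm, the unpooled standard error is √(0.6×0.4/120 + 0.4×0.6/120) = 0.0632. Then 0.20/0.0632 − 1.96 = 1.20, which gives 88.5% power (87.7% with pooled variance). This agrees with the stated 89%. The point here uses only N = 120.

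**Interval under the SAP rule.** At p = 0 the half-width is 1.96 × √(0 × 1/120) = 0, so the interval is 0% to 0%. At p = 1 it is 100% to 100%. The width is zero whatever N is.

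**Exact limits.** The two-sided 95% Clopper-Pearson upper limit at 0 responders is 1 − 0.025^(1/N), and the lower limit at N responders is 0.025^(1/N). The Wilson upper limit at 0 responders is z²/(N + z²).

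| Observed | SAP rule | Clopper-Pearson | Wilson |
|---|---|---|---|
| 0/120 | 0% to 0% | 0% to 3.03% | 0% to 3.10% |
| 120/120 | 100% to 100% | 96.97% to 100% | 96.90% to 100% |

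With fewer evaluable subjects the exact upper limit rises a little: 3.30% at N = 110 and 3.62% at N = 100.

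**Chance of a zero count,** (1 − π)^120: 30% at π = 1%, 9% at 2%, 2.6% at 3%, 0.2% at 5%.

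**Coverage at N = 120 and a true rate of 1%.** The SAP interval misses 1% when the count is 0 (probability 0.299). Counts 1 to 5 give intervals that contain 1%. At 6 the lower limit is 1.1%, so it misses again (6 or more: probability 0.001). Coverage is 1 − 0.299 − 0.001 = 0.70. By the same enumeration Clopper-Pearson covers 99% and Wilson 97%.

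**Ordinary rates.** At 48/120 (40%) the SAP interval is 31.2% to 48.8% and the exact interval 31.2% to 49.3%. Nothing material is wrong away from the boundary.

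**The case against.** The strongest reply is that this is a matter of presentation, and on scope that is right.

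- **Inference.** A reader might infer that the efficacy comparisons inherit the zero-width rule. They do not. The primary, key secondary and other binary treatment comparisons use the adjustment in SAP 5.2.1.1.
- **Small strata and subgroups.** A reader might take the rule into the smaller stratum, planned at 24 per arm, where the exact limit at 0/24 would be 1 − 0.025^(1/24) = 14.2%. The SAP plans no such table. Section 5.2 displays are by treatment group and time point. The subgroup analyses in SAP 6.4 report intervals for differences, and cells at 0% or 100% are sent to the SAP 5.2.1.1 adjustment.
- **The standard error of 0.** A reader might count this line in SAP 5.2.1.1 as a second false interval. It applies only when both arms in both strata are at the boundary and no comparison is made. What remains is an inconsistency: Section 5.2 reports NA at the boundary and Section 5.2.1.1 reports 0.
- **Frequency.** The documents give no expected rates for the strict endpoints, so how often a zero count will occur is a judgement. It is not expected for ASAS20 at Week 16, where 40% is assumed on placebo.
- **Mitigation.** The same table prints N, the number of responders and an NA standard error, so an alert reader can see the problem.

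The mitigation does not rescue the rule. An NA beside a zero-width interval is contradictory, and the column would still be labelled as a 95% confidence interval.

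**Conclusion.** The concern holds for the descriptive by-arm displays and no further. As written, the plan prints a zero-width 95% interval wherever an arm's observed rate at a visit is 0% or 100%. With 120 evaluable subjects the omitted uncertainty is about 3 percentage points, slightly more with missing data. The 70% coverage figure rests on an assumed true rate of 1%; at a true rate of 5% a zero count is so rare that the boundary rule hardly matters. No treatment difference, p-value, subgroup difference or Type I error statement changes. The correction is worth making because the rule is explicit, its output is wrong and the repair is trivial.

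**What to change.** In SAP 5.2, replace the boundary sentence with a rule that single-arm response rates carry Clopper-Pearson (or Wilson) 95% limits, at least in cells at 0% or 100%. Using one method for all single-arm rates is tidier. If only the boundary cells change, 0/120 would have an upper limit of 3.0%, while 1/120 would keep its normal-approximation limit of 0.83% + 1.96 × √(0.0083 × 0.9917/120) = 2.5%, so the limit would fall as the count rises.

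Keep the boundary standard error as NA in SAP 5.2, and change the 0 in SAP 5.2.1.1 to NA so that the two agree. Leave the 0.5 and 1 adjustment for treatment differences as it is.

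The cost is one SAP sentence, one changed entry and a standard software option. Descriptive intervals become slightly wider and asymmetric near the boundaries. Sample size, tests and the testing hierarchy are untouched.
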